### 3.2 SCHEDULE OF STUDY PROCEDURES

**Table 1 Schedule of Study Procedures**

	Screening	D0	D7	D28	D42
Informed Consent	X				
Confirmation of Eligibility Criteria	X	X			
History and physical	X	X		X	
Vitals (Day 42- Heavy Drinker group only)	X	X		X	X
Randomization (Heavy Drinker group only)		X			
Telephone Visit (Heavy Drinker group only)			X		
Alcohol consumption history	X	X		X	
Concomitant medications Assessment (Day7 & 42 -Heavy Drinker group only)	X	X	X	X	X
Adverse Event Assessment (Day7 & 42 -Heavy Drinker group only)		X	X	X	X
Electrocardiogram (Heavy Drinker group only)	X			X	
Dispense Study Medication (Heavy Drinker group only)		X			
Evaluation of study drug compliance (Heavy Drinker group only)			X	X	
CBC with Diff, CMP, PT/ INR Safety labs (Day 28 & 42- Heavy Drinker group only)	X	X		X	X
Urinalysis	X				
Urine Pregnancy test (if applicable)	X	X		X	
Hepatic CYP2E1 measurement study		X		X	
Gut Permeability Test		X		X	
Collection of Research Blood Samples for special investigations 		X		X	
Collection of stool specimen (optional) 		X		X	

Special Investigation Research samples collected for this protocol consist of FGF19, C4, fasting bile acid pool, adipocyte function (fasting NEFA, insulin, adiponectin), oxidative stress (malondialdehyde, 8-isoprostanate), bacterial translocation (plasma LPS, serum sCD14), cytokine measurements (serum TNF- $\alpha$ , IL-1, IL-6 and IL-8) and stool for calprotectin

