## **Overdosage**

The maximum dose of OCA that has been given to humans is 500 mg as a single dose and 250 mg as a multiple dose. Reversible increases in aminotransferases were seen in most of the healthy volunteers who took 250 mg OCA. There is no specific information available regarding the treatment of possible overdose with OCA. If overdose occurs in a patient enrolled in the trial, general medical supportive measures should be provided, including observation and follow up (e.g., serum chemistry) as appropriate. Due to the extensive enterohepatic recirculation of the drug it is likely that it will take several days before blood (and organ) concentrations of the drug will decrease. Treatment with cholestyramine (Questran™), colestevam (Welcol™) and other bile acid sequestrants is both logical and recommended given that they should bind and eliminate the drug in feces. Although there is no experience with OCA, plasmapheresis might be expected to reduce circulating levels of the drug. The study physician ([name] or designee) should be notified immediately in the event of a significant overdose.

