## **7.5 ELECTROCARDIOGRAM**

Standard 12-lead ECGs will be collected. The investigator or designee will review the 12-lead ECG and findings will be recorded in the CRF as normal, abnormal but not clinically significant, or abnormal and clinically significant. Any clinically significant abnormalities on ECGs recorded after Day 0 will also be documented as AEs and entered on the AE page of the CRF.

Investigative sites must retain a copy of all 12-lead ECGs evaluated by the investigator or designee. These ECGs must be clearly labeled with the subject's initials, Participant or Study ID Number, date and time.

The ECG read will be completed by the investigator or designee. At a minimum the following will be assessed: PR, QRS, QT and QTc intervals and a clinical evaluation for each ECG will be provided.

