## **8. ADVERSE EVENTS**

### **7.1 DEFINITION AND REPORTING PERIOD FOR ADVERSE EVENTS**

Safety will be assessed in terms of AEs. All AEs, whether observed by the investigator, reported by the subject, noted from laboratory findings, or identified by other means, will be recorded from the time the patient signs the ICF until the patient completes trial participation.

AEs are defined as any untoward medical occurrence associated with the use of the study medication in humans, whether or not considered related to study medication. An AE (also referred to as an adverse experience) can be any unfavorable and unintended sign (e.g., an

abnormal laboratory finding), symptom, or disease temporally associated with any use of the study medication, without any judgment about causality and irrespective of route of administration, formulation, or dose, including an overdose. For this trial, study medication refers to OCA.

AEs include, but are not limited to: (1) a worsening or change in nature, severity, or frequency of condition(s) present at the start of the trial; (2) subject deterioration due to primary illness; (3) intercurrent illness; and (4) drug interaction.

Subjects should be questioned in a general way, without leading the patient or asking about the occurrence of any specific symptom. The investigator should attempt to establish a diagnosis of the event based on signs, symptoms, and/or other clinical information. The diagnosis and not the individual signs/symptoms should be documented as the AE. For example, if the underlying disease process is a stroke, it would not be appropriate to record the AE by describing the symptoms "sudden numbness, dizziness, and difficulty speaking." The AE medical term of "stroke or cerebrovascular accident" should be recorded as it more accurately describes the AE.

Following questioning and evaluation, all AEs, whether believed by the investigator to be related or unrelated to the study medication, must be documented in the subject's medical records, in accordance with the investigator's normal clinical practice and on the AE CRF. Each AE is to be evaluated for duration, intensity, frequency, seriousness, outcome, other actions taken, and relationship to the study medication.

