### **9.2 Longitudinal component:**

**Primary endpoint:** In the intervention phase, the main goal is to see whether OCA will alternate or reverse the C4(FGF19). So the main analysis to use two-sample t-test to compare the change of C4(FGF19) from baseline to 4 weeks between the randomized treated and placebo arm. The secondary analysis for the primary end points is to compare the C4 (FEF19) level at 4 week using two-sample t-tests to see whether the C4 level of the treated group has recover to the normal control level after 4 weeks treatment.

**The secondary endpoint** will be compared using two-sample t-tests in a similar way to the primary endpoints.

**Power analysis:** For the intervention study, there are 15 subjects in each group. We use two-sample t-test for comparison of the change of C4 and FGF19. With these sample size, we will have 82% power to detect any difference in change of C4(or FGF19) of effect size equal to or greater than 1.11(mean/SD) with a 5% Type I error rate.

**9.3 Safety Analysis:** Descriptive statistics will be used to summarize the AEs if occur.

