#### **Adverse Events**

AEs will be coded using the Medical Dictionary of Regulatory Activities (MedDRA). Summary tables of treatment-emergent AEs will be provided. A TEAE is any AE that newly appeared, increased in frequency, or worsened in severity following initiation of study medication. The incidence of TEAEs will be tabulated by system organ class and preferred term for each treatment group, and by severity and relationship to treatment. Tables of TEAEs leading to study medication discontinuation and SAEs will be provided.

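### The safety analysis covers adverse events only: no by-arm summary is planned for the laboratory values and ECG intervals collected in the randomised heavy drinkers, so a shift not recorded as an AE may be missed

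*Combined protocol and SAP*

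**What the plan says.** The adverse-event section (8, subsection 7.1) sets the scope: "Safety will be assessed in terms of AEs". Section 9.3 follows it: "Descriptive statistics will be used to summarize the AEs if occur". The Adverse Events paragraph after 9.3 gives the content: "The incidence of TEAEs will be tabulated by system organ class and preferred term for each treatment group", with breakdowns by severity and relationship, and tables of SAEs and of events leading to discontinuation of study medication.

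Table 1 (section 3.2) schedules more safety data than that. The laboratory row reads "CBC with Diff, CMP, PT/ INR Safety labs (Day 28 & 42- Heavy Drinker group only" and is marked at Screening, Day 0, Day 28 and Day 42. The ECG row, "Electrocardiogram (Heavy Drinker group only", is marked at Screening and Day 28. Section 7.5 says what is read from each tracing: "At a minimum the following will be assessed: PR, QRS, QT and QTc intervals".

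Section 7.5 also says how an ECG finding reaches the AE record: "Any clinically significant abnormalities on ECGs recorded after Day 0 will also be documented as AEs". For laboratory values, subsection 7.1 counts an abnormal laboratory finding among possible AEs. Section 7.4 uses clinical significance to trigger follow-up of a patient, and section 8.7 mentions clinically significant laboratory values among the AEs to be followed.

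**The concern.** The randomised, placebo-controlled part of the trial yields numeric safety data before treatment, at the end of treatment and, for the laboratory values, two weeks later. The written analysis uses them only where someone has recorded an AE. A consistent change in one arm, with each patient's value unremarkable on its own, would appear in no planned table. Nor would recovery between Day 28 and Day 42.

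The liver is a relevant organ to examine. Section 1.2 reports liver and gastrointestinal effects in animals, and the Overdosage paragraph in section 6.4 says: "Reversible increases in aminotransferases were seen in most of the healthy volunteers who took 250 mg OCA". Both need their context: the animal effects were confined to the highest doses, and 250 mg is 25 times the 10 mg used here. They point to an organ; they do not predict harm at the trial dose. Section 1.1 adds that FXR agonists had not been studied in heavy drinkers, and the entry criteria admit drinkers with ALT and AST up to 100 U/L. Some raised values at baseline are therefore possible, and change from baseline by arm is the natural way to separate a drug effect from them.

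At stake is the tolerability conclusion. A report that followed the plan could describe OCA as well tolerated without having looked at these values by arm.

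**Working it through.** **1. Is a by-arm summary planned anywhere else?**

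| Place | What it covers | Safety labs or ECG by arm? |
|---|---|---|
| 9.2, secondary endpoints | Bile salts, oxidative stress, CYP2E1, gut and immune markers | No |
| Synopsis, Study Measurements table | Uses a clinical laboratory heading, but lists those markers, adipocyte function, AEs and SAEs | No |
| 9.3 and Adverse Events paragraph | AEs, SAEs, discontinuations | Only findings recorded as AEs |
| 7.4 and 8.7 | Follow-up of individual patients | No |
| DSMB paragraph | Periodic review of safety data, content left to a charter | Not specified |
| 5.2 | Refers to an SAP for the definition of baseline | Nothing further in the combined document |

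The gap is confirmed on the text.

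**2. The plan's own power figures.** Inputs from 9.1 and 9.2: 15 v 15 at 1.11 SD (stated 82%) and 15 v 30 at 0.95 SD (stated 83%), 5% type I error, taken here as two-sided. Noncentrality = d / √(1/n₁ + 1/n₂).
- 15 v 15: 1.11 / √(2/15) = 3.04, 28 df, critical t 2.048, power 83.5%.
- 15 v 30: 0.95 / √(1/15 + 1/30) = 3.00, 43 df, critical t 2.017, power 83.6%.

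Both agree with the stated figures to within 2 points. They are not in dispute; they confirm the 15 v 15 structure available for a safety comparison.

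**3. What a by-arm summary could show.** Half-width of the 95% CI for the OCA minus placebo difference in mean change = t(0.975, 2n−2) × √(2/n), in units of the SD of change.
- n = 15 per arm: 2.048 × 0.365 = 0.75 SD.
- n = 13 (assumed loss): 2.064 × 0.392 = 0.81 SD.
- n = 12 (assumed loss): 2.074 × 0.408 = 0.85 SD.

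For a single variable at 15 per arm, two-sided t-test power is 26% for a 0.5 SD shift, 56% for 0.8 SD and 75% for 1.0 SD. Only large shifts are likely to stand out.

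**4. Chance findings.** The documents do not count the variables. If there were 25 to 50 comparisons (assumed), 0.05 × 25 = 1.25 to 0.05 × 50 = 2.5 intervals would be expected to exclude zero with no drug effect.

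**5. Could AE recording pick up a shift? Illustration only.** Assume normal values, a 1.0 SD shift on OCA, and an AE recorded whenever a value passes a cut-off. None of this is in the documents.
- Cut-off 3 SD above the baseline mean: 1 − Φ(2) = 2.3% of OCA patients cross, 15 × 0.0228 = 0.34 expected, and the chance that none does is 0.977¹⁵ ≈ 71%.
- Cut-off at the placebo 95th percentile: 1 − Φ(1.645 − 1) = 26% cross, 15 × 0.26 = 3.9 expected against 0.75 on placebo, and the chance that none does is 0.74¹⁵ ≈ 1%.

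So the answer depends almost wholly on where the threshold lies, and the protocol does not state one for laboratory values.

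**The case against.** **Laboratory findings are not shut out.** A reader might infer that a laboratory change counts only if judged clinically significant. The text makes that condition explicit for ECGs alone. Subsection 7.1 lets an abnormal laboratory finding be an AE, and such AEs are tabulated by arm. This stands, so the claim must be limited to shifts not recorded as AEs.

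**The loss of sensitivity cannot be given as one number.** It is tempting to set a t-test on means (75% power at 1.0 SD, 15 v 15) against Fisher's test on counts above the placebo 95th percentile (5% v 26%, power 19%). Those figures are arithmetically right. But the plan contains neither a Fisher test nor that cut-off, and under the same assumptions a descriptive AE table would be expected to show 3.9 events against 0.75. The comparison does not show that the plan would miss the shift.

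**The documents do not forbid the comparison.** A reader might infer that the values will never be compared. The plan is silent, the DSMB will see safety data, and an SAP is mentioned. This supports saying that no summary is planned and that a shift may be missed, but no more. An unspecified DSMB review is not a reported analysis.

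**The liver signal is from other doses.** This stands, as does the point that section 1.4 names pruritus as a major issue, which AE tables do capture. Neither removes the reason to summarise values that are being collected anyway.

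**Many intervals invite false alarms.** This also stands, and it is why the added output should be descriptive.

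**Conclusion.** The point holds as a gap in the planned safety analysis. The text limits the safety output to AEs, while CBC, CMP, PT/INR and ECG intervals from the 30 randomised drinkers have no planned summary by arm. A shift not recorded as an AE may be missed. For ECGs the route to an AE requires clinical significance; for laboratory values sections 7.1, 7.4 and 8.7 leave the threshold unclear.

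The gain from closing the gap is real but modest. At 15 per arm a difference in mean change is estimated to within about ±0.75 SD, or ±0.81 to ±0.85 SD if 12 or 13 per arm remain (assumed). This rests on roughly normal changes with similar spread in both arms. The documents do not show that a shift would be missed, nor that harm to the liver is expected at 10 mg. The efficacy conclusions are unaffected. The change should be made because it costs little and bears on any tolerability statement.

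**What to change.** Add to section 9.3, by randomised arm, labelled descriptive and without multiplicity-controlled testing:
- observed values at each visit, and mean change with 95% CI, for each CMP, CBC and INR variable from Day 0 to Day 28 and from Day 0 to Day 42;
- the same for PR, QRS, QT and QTc from Screening to Day 28;
- shift tables of the worst post-baseline laboratory value against normal limits.

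Adjustment for the baseline value is optional and applies to the mean changes only; a shift table already sets baseline against follow-up. State beside the tables that the intervals are wide and that some will exclude zero by chance.

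The cost is a few extra tables and some chance findings to read with caution. No new visits, samples or patients are needed, and no dose or clinical rule is affected.

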#### **Adverse Events**

AEs will be coded using the Medical Dictionary of Regulatory Activities (MedDRA). Summary tables of treatment-emergent AEs will be provided. A TEAE is any AE that newly appeared, increased in frequency, or worsened in severity following initiation of study medication. The incidence of TEAEs will be tabulated by system organ class and preferred term for each treatment group, and by severity and relationship to treatment. Tables of TEAEs leading to study medication discontinuation and SAEs will be provided.

#### **HANDLING OF MISSING DATA**

Missing values will not be imputed and only observed values will be used in data analyses and presentations.

#### **DATA AND SAFETY MONITORING BOARD (DSMB)**

A local DSMB (to be announced) will be formed to review safety data at periodic intervals from this trial. Members of the DSMB will not be allowed to participate as investigators in this trial and will not otherwise consult for the Sponsor.

The DSMB will review safety data to ensure the safe and proper treatment of patients. Based on review of these data, the DSMB will advise the Sponsor on the validity and scientific merit of continuing the trial.

The DSMB will operate under an appropriate charter (in compliance with relevant regulatory guidances) that will define its organization and operation. The DSMB will prepare written minutes of both its open and closed sessions.

All investigators and responsible IRB will be informed of any decisions made by the Sponsor based on recommendations from the DSMB relating to patient safety, which alter the conduct of this trial. The investigators will inform the patients of such actions and the protocol and ICF will be revised, as appropriate.

## **10. ADMINISTRATIVE AND REGULATORY CONSIDERATIONS**

### **10.1 ETHICAL CONDUCT OF THE TRIAL**

This trial will be conducted in accordance with 21CFR Part 312, Good Clinical Practice (CPMP/ICH/135/95), and with the ethical principles laid down in the Declaration of Helsinki and applicable regulatory requirements.

### **10.2 INSTITUTIONAL REVIEW BOARD (IRB)**

A properly convened IRB at each participating site will review and approve this study prior to its initiation. All protocol amendments will be reviewed and approved by the IRBs. Amendments can be implemented only following the IRB approval unless the amendment is necessary to reduce immediate risk to trial participants.

The IRB will be informed of any new safety information that negatively affects the risk assessment of the trial as soon as it becomes available.

Investigators or the Sponsor or its designee will provide reports to the IRB/IEC as requested, as a minimum annually, and after the trial is complete.

### **10.3 PATIENT CONFIDENTIALITY AND DATA PROTECTION**

All information obtained during the conduct of the trial with respect to the patient will be regarded as confidential and confidentiality of all patients will be maintained. Monitors, auditors and inspectors will require access to a patient's medical notes for the purpose of source document verification but the patient's confidentiality will be maintained at all times. An agreement for disclosure of any such information will be obtained in writing and is included in the statement of informed consent. The trial data shall not be disclosed to a third party (with the exception of auditors, Intercept as the supporter and/or regulatory authorities) without the written consent of the Sponsor. All data shall be secured against unauthorized access.

Apart from the site investigators, no one will have access to participant's identify. Each site will securely maintain the code that links participants' identity to their study numbers to prevent access to unauthorized third parties. Participants will be identified according their study numbers in the data management system (OnCore) and by the investigators during any communications.

The written ICF will explain that, for data verification purposes, authorized representatives of Intercept (the supporter), a regulatory authority, or an IEC / IRB may require direct access to parts of the hospital or practice records relevant to the trial, including patient's medical history.

### **10.4 ACCESS TO SOURCE DOCUMENTS AND DATA**

#### **Source documents**

Source documents may include, but are not limited to, medical records, charts, appointment books, patient questionnaires, original laboratory records, equipment print-outs. All source documents must be made available to the CRA. The following data must be included in the source data:

- (a) consent to participate in Trial
- (b) patient visit dates
- (c) Screening and Randomization Numbers
- (d) demographic information
- (e) medical history
- (f) disease history
- (g) physical examination
- (h) vital signs
- (i) laboratory assessments (copy of laboratory reports)
- (j) AEs and concomitant medications
- (k) dates of dispensing study medication
- (l) ECGs
- (m) patient questionnaires
- (n) drug accountability
- (o) issues with protocol compliance
- (p) completion of, or withdrawal from, trial

### **Case Report Forms**

A CRF to capture trial data will be completed by trial site staff for each patient who has signed the ICF and is assigned a patient number. The CRF may be developed in paper format or within an electronic data capture (EDC) system. Data management vendors will be detailed within a separate trial document.

The CRF must be completed promptly after each patient visit.

